# 8.2 Exclusion Criteria (Treatment Cohort Only)

- 1. Prematurely discontinued LUM/IVA treatment in Study 115B.
- 2. History of any comorbidity or laboratory abnormality that, in the opinion of the investigator, might confound the results of the study or pose an additional risk in administering LUM/IVA to the subject (e.g., cirrhosis with portal hypertension).
- 3. History of drug intolerance or other serious reactions to LUM/IVA in Study 115B that would pose an additional risk to the subject in the opinion of investigator, and which should be discussed with the Vertex medical monitor.
- 4. Subjects with a history of allergy or hypersensitivity to LUM/IVA.
- 5. Liver function test (LFT) abnormality meeting criteria for LUM/IVA treatment interruption at the completion of Study 115B, for which no convincing alternative etiology is identified.
- 6. QTc value at the completion of Study 115B that would pose an additional risk to the subject in the opinion of investigator, and which should be discussed with the Vertex medical monitor (e.g., remained above the threshold value [>45 msec from baseline or >500 msec] on

- repeated measurement or was noted on 2 or more occasions with no identified alternative etiology for the increased QTc).
- 7. History of poor compliance with LUM/IVA and/or procedures in Study 115B as deemed by the investigator.
- 8. Participation in an investigational drug trial (including studies investigating LUM and/or IVA) other than Study 115B. NOTE: participation in a non-interventional study is permitted (including observational studies, registry studies, and studies requiring blood collections without administration of study drug).

### 9 STUDY IMPLEMENTATION

[figure not shown]
### 9.1 Study Design

This is a Phase 3, open-label, multicenter study with a Treatment Cohort and an Observational Cohort (Figure 9-1).

[figure not shown]
Procedural details are described in Sections 9.1.1 and 9.1.3.

Figure 9-1 Schematic of Study Design

#### Treatment Cohort

#### Observational Cohort

ETT: Early Termination of Treatment; IVA: ivacaftor; LUM: lumacaftor; q12h: every 12 hours

- Doses may be adjusted upward for changes in weight and age. See the rules for dose adjustments in Section 9.6.
- Doses are those planned for Study 115B. Based on results from Study 115A and 115B, doses for subjects <6 years of age in Study 116 may be modified.

- The Safety Follow-up Visit is required for 1) subjects who complete their ETT Visit <10 days after the last dose of LUM/IVA (Section 9.1.2.3); and 2) subjects who interrupt LUM/IVA treatment and complete their Week 96 Visit <10 days after the last dose of LUM/IVA; it is not required for subjects who continue onto commercially-available, physician-prescribed LUM/IVA within 2 weeks (± 4 days) of completing LUM/IVA treatment at the Week 96 or ETT Visit.
- See Section 9.1.1 for details regarding the timing of the Day 1 Visit.

### 9.1.1 Timing of Study 116 Day 1 Visit

#### 9.1.1.1 Treatment Cohort and Observational Cohort

For subjects at sites activated by the time of their applicable Study 115B visit (i.e., the Safety Follow-up Visit for subjects in the Treatment Cohort and the Week 24 Visit or the Safety Follow-up Visit, if required, for subjects in the Observational Cohort), their Study 116 Day 1 Visit will be on the same day as their applicable Study 115B visit, and any Study 116 Day 1 assessments that were specified to be performed at the applicable Study 115B visit do not need to be repeated. If the Study 116 Day 1 Visit does not coincide with the subject's applicable Study 115B visit, the subject will complete all Study 116 Day 1 assessments (except the OE if it was performed within the last 3 months before the visit for subjects in the Treatment Cohort).

### 9.1.1.2 Treatment Cohort

Subjects at sites activated by the time of their applicable Study 115B visit (Section 9.1.1.1) may return within 1 calendar day to complete the remaining Day 1 assessments specific to Study 116 (including administration of the Day 1 dose). Predose vital sign and spirometry assessments must be repeated before dosing on the following calendar day.

Subjects who were enrolled but had Day 1 LUM/IVA administration procedures (Section 9.6) delayed more than 1 calendar day will repeat all assessments that were specified to be performed at the Day 1 visit before receiving their first dose of LUM/IVA (except for the OE if it was performed within the last 3 months before the visit).

#### 9.1.2 Treatment Cohort

#### 9.1.2.1 Treatment Period

To prepare for study participation, subjects will be instructed on the study restrictions (Section 9.4).

Treatment Period assessments are listed in Table 3-1. Subjects will be outpatients during the Treatment Period. All visits should occur within the windows specified.

The Treatment Period is 96 weeks; LUM/IVA will be administered every 12 hours (q12h) from Day 1 through Week 96. The dose before the Week 96 Visit will be the last dose. Administration and management details are provided in Sections 9.6 and 10.

Procedures for subjects who prematurely discontinue LUM/IVA treatment are described in Section 9.1.2.3.

### 9.1.2.2 Follow-up

The Safety Follow-up Visit is required for 1) subjects who complete their Early Termination of Treatment (ETT) Visit <10 days after the last dose of LUM/IVA (Section 9.1.2.3); and 2) subjects who interrupt LUM/IVA treatment and complete their Week 96 Visit <10 days after the last dose of LUM/IVA; it is not required for subjects who continue onto commercially-available, physician-prescribed LUM/IVA within 2 weeks ( $\pm$  4 days) of completing LUM/IVA treatment at the Week 96 or ETT Visit.

The Safety Follow-up Visit is scheduled to occur 2 weeks ( $\pm$  4 days) after the last dose of LUM/IVA. Safety Follow-up Visit assessments are listed in Table 3-1.

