#### 8.1 Inclusion Criteria

1. Subject's legally appointed and authorized representative (e.g., parent or legal guardian) will sign and date an informed consent form (ICF) and the subject will sign and date an assent form (if applicable).

- 2. Subjects entering the **Treatment Cohort** must meet the following criteria:
  - Completed 24 weeks of LUM/IVA treatment and the Safety Follow-up Visit in Study 115B
    - Subjects who had study drug interruptions are eligible if they completed study visits up to the Safety Follow-up Visit of Study 115B. Subjects who are not taking LUM/IVA at the end of the Study 115B Treatment Period (i.e., Week 24), including subjects who have LUM/IVA treatment temporarily interrupted as of Day 1 in Study 116, must receive Vertex approval for enrollment in the Treatment Cohort.

Subjects entering the **Observational Cohort** must meet 1 of the following criteria:

- Completed 24 weeks of LUM/IVA treatment and the Safety Follow-up Visit in Study 115B, but do not want to enroll in the Treatment Cohort.
- Received at least 4 weeks of LUM/IVA treatment and completed visits up to Week 24 and the Safety Follow-up Visit, if required, of Study 115B but are not taking LUM/IVA at the end of the Study 115B Treatment Period (i.e., Week 24) because of a drug interruption and either did not receive Vertex approval to enroll in the Treatment Cohort or do not want to enroll in the Treatment Cohort.
- Permanently discontinued LUM/IVA in Study 115B after receiving at least 4 weeks of treatment and remained in the study from the time of treatment discontinuation through the Week 24 Visit and Safety Follow-up Visit, if required.
- 3. Willing to remain on a stable CF medication regimen through the Safety Follow-up Visit (Treatment Cohort only).
- 4. As deemed by the investigator, the subject's legally appointed and authorized representative (e.g., parent or legal guardian) must be able to understand protocol requirements, restrictions, and instructions. The subject's legally appointed and authorized representative should be able to ensure that the subject will comply with, and is likely to complete, the study as planned.

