### 9.1.2.3 Early Termination of Treatment

Subjects who prematurely discontinue LUM/IVA treatment will be asked to complete the ETT Visit as soon as possible after the last dose of LUM/IVA. The assessments to be completed are listed in Table 3-1. If the ETT Visit occurs 10 days or later following the last dose of LUM/IVA, then the ETT Visit will replace the Safety Follow-up Visit, (i.e., the assessments performed will be those specified for the ETT Visit), and a Safety Follow-up Visit will not be required.

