### 9.5.2 Prior and Concomitant Medications

It is recommended that subjects remain on a stable medication regimen for their CF from Study 115B through the Safety Follow-up Visit in Study 116. Stable medication regimen is defined as the current medication regimen for CF that subjects have been following for at least 28 days before Day 1 of Study 115B.

Subjects who are using a bronchodilator should have their LCI and spirometry assessments performed according to the guidelines provided in Section 11.6.7.

Information regarding all prior and concomitant medications, including the subject's CF medications, other medications, and herbal and naturopathic remedies administered at, or after, the Safety Follow-up Visit in Study 115B through the Safety Follow-up Visit of this study will be recorded in each subject's source documents. In addition, concomitant medication dose(s) may be collected.

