### Discontinuation of Study Drug

If no convincing alternative etiology (e.g., acetaminophen use, viral hepatitis, or alcohol ingestion) for the elevated transaminases is identified, regardless of whether ALT or AST levels have improved, LUM/IVA treatment must be discontinued, after consulting with the Vertex medical monitor or authorized designee. Subjects in whom treatment is discontinued for elevated transaminases should have their transaminases monitored closely until levels normalize or return to baseline.

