## **Study Drug Compliance**

Study drug compliance will be calculated as follows:  $100 \times (1 - [total number of days of study drug interruption in the Cumulative Study Period] / [duration of study drug exposure in the Cumulative Study Period). The total number of days of study drug interruption is defined as the$ 

sum of (number of days of each study drug interruption in the Cumulative Study Period), where number of days of each study drug interruption is defined as the interruption end date – the corresponding interruption start date + 1.

Treatment compliance percentages will be summarized descriptively (number, mean, SD, median, minimum, and maximum) overall based on Safety Set for the Cumulative Study Period. The number and percentage of subjects whose compliance is <80% or ≥80% will be summarized.

- 12.3.3 Pharmacodynamic Analysis
- 12.3.3.1 Analysis of Primary Variables

Not applicable

- 12.3.3.2 Analysis of Secondary Pharmacodynamic Endpoints
- 12.3.3.2.1 Absolute Change from Baseline: Sweat Chloride, BMI, BMI-for-Age Z-score, Weight, Weight-for-Age Z-score, Stature, Stature-for-Age Z-score, and LCI

For the secondary endpoint of sweat chloride, raw and absolute change from the Cumulative Study Baseline in sweat chloride at each visit in the Cumulative Study Period (including all measurements from Study 115B and Study 116, including the Safety Follow-up Visit of Study 116, both on-treatment measurements and measurements after treatment discontinuation), will be summarized based on FAS. Descriptive statistics including number of subjects, mean, SD, SE, median, minimum, and maximum, along with the 95% CI and within-group *P* value based on Normal approximation, will be provided for the absolute change from the Cumulative Study Baseline. The mean (95% CI) of the absolute change from baseline will be plotted. The following secondary endpoints will be summarized similarly as described above for sweat chloride based on FAS:

- Absolute change from Cumulative Study Baseline in BMI and BMI-for-age z-score
- Absolute change from Cumulative Study Baseline in weight and weight-for-age z-score
- Absolute change from Cumulative Study Baseline in stature and stature-for-age z-score
- Absolute change from Cumulative Study Baseline in LCI2.5
- Absolute change from Cumulative Study Baseline in LCI5.0

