#### **10.2.5 Study Drug Compliance**

Study drug compliance will be summarized for the Current Study Period based on 116 Safety Set.

Study drug compliance will be calculated for the Current Study Period as follows:  $100 \times (1 - [\text{Total number of days of study drug interruption in Current Study Period}] / [\text{Duration of study drug exposure in Current Study Period} + \text{Total number of days study drug interrupted after last dose in Current Study Period, if any}])$ . The total number of days of study drug interruption is defined as the sum of (number of days of each study drug interruption in the Current Study Period), where number of days of each study drug interruption is defined as the interruption end date – the corresponding interruption start date + 1.

Treatment compliance percentages will be summarized descriptively (number, mean, SD, median, minimum, and maximum). The number and percentage of subjects whose compliance is <80% or ≥80% will be also be summarized.

In calculating the total number of days of study drug being interrupted, only the interruptions with duration of ≥3 days will be considered. An interruption with duration of < 3 days will not be considered in the calculation.

Study drug exposure and compliance data for each subject will also be listed.

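### Read literally, the Safety Follow-up rule requires no off-drug visit for a child who takes every dose to Week 96 and does not move to commercial LUM/IVA

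*Protocol*

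**What the plan says.** Protocol Section 9.1.2.2 has two limbs and a waiver.

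- Limb 1 requires the Safety Follow-up Visit when the Early Termination of Treatment (ETT) Visit falls fewer than 10 days after the last dose.
- Limb 2 requires it for "subjects who interrupt LUM/IVA treatment and complete their Week 96 Visit <10 days after the last dose of LUM/IVA".
- The waiver excuses children who go on to commercial LUM/IVA within 2 weeks (± 4 days) "of completing LUM/IVA treatment at the Week 96 or ETT Visit".

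The same sentence is in Protocol Table 3-1 (footnote c), the Figure 9-1 footnotes, SAP Figure 7-1 (footnote c) and SAP Appendix A, Table 13-1 (footnote c).

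Section 9.1.2.3 adds that if the ETT Visit is 10 days or more after the last dose, "then the ETT Visit will replace the Safety Follow-up Visit". Sections 9.1.2.1 and 9.6 make the dose before the Week 96 Visit the last one for everybody still on treatment.

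**The concern.** Limb 2 joins two conditions: treatment was interrupted, and the Week 96 Visit came within 10 days of the last dose. A child who never missed a dose fails the first condition. Having had no ETT Visit, that child fails limb 1 as well. No other section supplies the requirement.

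The primary objective is long-term safety, and this is the only scheduled visit after drug is stopped. Under the literal rule, the fully adherent completer not moving to commercial drug would have no scheduled assessment off drug after Study 116 treatment. Sweat chloride, LCI, FE-1 and IRT are also not collected at the ETT Visit. Their off-drug values after Study 116 treatment would come only from children with interruptions and from early terminators whose ETT Visit was fewer than 10 days after the last dose. That is an unrepresentative group.

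**Working it through.** **What *interrupt* means in these documents**

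- Protocol Section 11.6.3 treats interruption, resumption and discontinuation under separate headings. If no other cause is found, "regardless of whether ALT or AST levels have improved, LUM/IVA treatment must be discontinued", which is a different action from the earlier hold.
- Protocol Section 12.3.2.4 counts each interruption from dates, "where number of days of each study drug interruption is defined as the interruption end date" minus its start date plus 1. An interruption is therefore a bounded gap.
- Protocol Table 13-3 codes an interrupted drug separately from a permanently withdrawn one.
- SAP Section 10.2.5 adds "Total number of days study drug interrupted after last dose in Current Study Period, if any" to its denominator, so a hold can still be open at the end of treatment.
- The 10-day test fits this reading. A child who doses to the end is under 1 day from the last dose at Week 96, so the test sorts only children on hold.

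**The plan's own figures**

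- Follow-up window: 14 ± 4 = day 10 to day 18 after the last dose. The upper edge equals the 18-day limit in Section 13.1.1.3.
- Target day: 673 + 14 = 687, as in SAP Table 13-3.
- Study duration: 96 + 2 = 98 weeks, as in the synopsis.
- Expected enrollment: 56 × 0.90 = 50.4, stated as 50 in Section 12.1.

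**The rule applied case by case**

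Required = (limb 1 or limb 2) and not continuing on commercial drug, with *interrupt* taken as a hold.

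| Child | Required as written | Required without the interruption condition |
|---|---|---|
| ETT Visit 3 days after last dose, no commercial drug | Yes | Yes |
| ETT Visit 12 days after last dose | No (ETT Visit replaces it) | No |
| ETT Visit 3 days after last dose, commercial drug | No | No |
| Interrupted, Week 96 at 3 days, no commercial drug | Yes | Yes |
| Interrupted, Week 96 at 12 days | No | No |
| **All doses taken, Week 96 at about 0.5 day, no commercial drug** | **No** | **Yes** |
| All doses taken, Week 96 at about 0.5 day, commercial drug | No | No |

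One case of seven changes. Among children not moving to commercial drug, it is the only one with no scheduled assessment at 10 or more days off drug. Its Week 96 Visit is more than 10 − 1 = 9 days before the follow-up window opens.

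**What one missed visit contains**

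The Safety Follow-up column of Table 3-1 lists stature and weight, vital signs, oximetry, full physical examination, ECG, chemistry, hematology, IRT, FE-1, sweat chloride, LCI, spirometry and other outcome events: 13 assessments. The eye examination is left out because one at Week 96 satisfies it. LCI is optional, and LCI and spirometry apply only to children aged 3 or more at Study 115B screening. All 13 are also done at Week 96. At the ETT Visit, 13 − 4 = 9 are done (not IRT, FE-1, sweat chloride or LCI).

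**Signs that the gap was not intended**

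- The waiver covers children completing treatment at Week 96. Fully adherent completers would need no waiver if the rule never reached them.
- The synopsis (Study Design) lists the visit without a condition.
- Section 9.5.2 recommends a stable CF regimen "from Study 115B through the Safety Follow-up Visit in Study 116", and inclusion criterion 3 and the SAE reporting rule in Section 13.1.2.2 run to the same visit.
- Protocol Section 12.3.2.1 and SAP Section 10.2.1 define study completion by that visit.

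The synopsis duration entry and the adverse-event row of Table 3-1 make the visit conditional, so they do not settle the matter.

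**The case against.** The best counter-argument is that limb 2 sets *interrupt* against continuing onto commercial drug in the same sentence, so the word means any break in treatment after Week 96. The waiver, the unconditional synopsis entry and the Day 687 target support that. Section 8.1 adds the qualifier *temporarily* when it means a hold, and the SAP allows interruption days after the last dose. The case table assumes the hold meaning, so it cannot decide between the readings.

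This is a good account of what was probably intended, but it does not rescue the wording. If *interrupt* means stopping study drug at Week 96, it adds nothing, because study dosing ends for everyone before that visit. If it means not going on to commercial drug, the waiver already says so. Deleting the phrase is right on either reading.

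The argument that the harm is small largely stands. Week 96 carries all 13 assessments within about a day of the last dose. Section 13.1.1.3 provides for children without a follow-up visit and collects adverse events to day 18, although its query is tied to study visits and none remains. Known adverse events are followed to outcome, and later related SAEs are still reported. No listed endpoint is a withdrawal effect. Study 115B also gives off-drug data, though after 24 weeks of treatment rather than 24 + 96 = 120.

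Many children may also be waived. From the start of Study 115B to Week 96 is 24 + 2 + 96 = 122 weeks, about 2.3 years. A child aged about 3.7 or more at the start would be 6 by then, and Section 5.1 gives US approval from age 6. But a child who started at 2 would be about 4.3, and the same section gives approval from age 12 in the other regions it names. The country mix is not stated.

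**Conclusion.** The concern holds on the literal text: the fully dosed completer not moving to commercial drug meets neither limb. For each such child the rule provides 0 scheduled assessments at 10 or more days off drug, against 1 for an early terminator not moving to commercial drug.

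The total effect cannot be computed. The number affected runs from 0 to below 50, because the 50 expected enrollees cover both cohorts and include children who leave early or move to commercial drug. It also depends on how each site reads the word. The likely practical result is inconsistent conduct, with some sites holding the visit and others not. Because this is an operative safety follow-up rule in a study whose primary objective is safety, it should be corrected. The limited loss per child makes it no more serious than that.

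**What to change.** In limb 2, delete the interruption condition, so that the limb covers all subjects whose Week 96 Visit falls fewer than 10 days after the last dose. Do this in Protocol Section 9.1.2.2, Table 3-1 and Figure 9-1, and in SAP Figure 7-1 and Appendix A. Keep the commercial-drug waiver.

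The cost is one short deletion repeated in five places and, per affected child, at most one visit already in the schedule.

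The definition of study completion by the Safety Follow-up Visit also leaves out children who are validly waived. That is a separate point which this change does not repair.

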### 9.1.2.3 Early Termination of Treatment

Subjects who prematurely discontinue LUM/IVA treatment will be asked to complete the ETT Visit as soon as possible after the last dose of LUM/IVA. The assessments to be completed are listed in Table 3-1. If the ETT Visit occurs 10 days or later following the last dose of LUM/IVA, then the ETT Visit will replace the Safety Follow-up Visit, (i.e., the assessments performed will be those specified for the ETT Visit), and a Safety Follow-up Visit will not be required.

### 9.1.3 Observational Cohort

Observational Cohort assessments are listed in Table 3-2. The Observational Cohort will include the following:

- Day 1 Visit
- Long-term follow-up telephone contacts at Weeks 48 and 96

Subjects who become eligible to receive commercially-available, physician-prescribed LUM/IVA, and who choose to continue onto commercially-available LUM/IVA, must have an Early Termination Telephone Contact to terminate their participation in the study.

### 9.1.4 Lost to Follow-up

A subject will be considered lost to follow-up if both of the following occur:

- Subject misses 2 consecutive study visits (telephone contact and/or clinic visit) and is subsequently unable to be contacted by telephone (3 documented attempts by telephone within 2 weeks following the second missed visit)
- Subject does not respond within 2 weeks to a registered letter sent after the 3 attempted telephone contacts

### 9.1.5 Independent Data Monitoring Committee

An independent data monitoring committee (IDMC) will be formed using the Cystic Fibrosis Foundation Data Safety Monitoring Board. The IDMC objectives and operational details will be defined in a separate document (IDMC Charter), which will be finalized before the first subject is enrolled. The IDMC will conduct regular planned reviews of study data for the purpose of safety monitoring as outlined in the IDMC Charter.

